## Statistical analysis

### *Primary end points*

The analysis of the primary end point will be performed under the intention-to-treat principle, and only include patients that have had a MAP below 65 mmHg for at least one minute during the procedure. As the study is an interrupted time series design, segmented regression models will be used for both primary end points. The different study groups within the nested cluster-randomized trial will not be separately analyzed because of a too small sample size.

A two-sided alpha of 0.05 will be considered to be statistically significant. Continuous variables will be visually assessed for a normal distribution using histograms and QQ-plots. In descriptive statistics, parametric variables will be expressed as means with standard deviations, nonparametric variables will be expressed as medians with interquartile ranges, and discrete variables will be expressed as numbers with percentages. Missing data will be multiply imputed

using a regression approach. Before multivariable modelling, all continuous variables will be tested for nonlinearity using restricted cubic splines.

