Clinical decision support may help anesthesia providers to adhere more strictly to their own clinically acceptable blood pressure thresholds. An automated notification system may alert the anesthesia providers when the blood pressure of their patient drops below 60 mmHg MAP. A recent randomized trial didn't demonstrate any change in blood pressure management as a result of automated blood pressure notifications. Because of the study design, the authors do not provide a satisfactory explanation of why it didn't change blood pressure management. Although randomization at the patient level may seem the appropriate thing to do, there is a serious risk of contamination. When on a given day an anesthesia provider received notifications for the first patient, is it likely that the provider will be more aware of the blood pressure threshold during a next case, even when the subsequent patient was randomized to the control group. The contamination could be one explanation for a 'null-result' for the study. Another explanation would be that the authors did not provide sufficient context to the notifications, which has been suggested to be a requirement for the successful implementation of decision support. The recent randomization trial thus by no means provides sufficient scientific evidence that clinical decision support for IOH does not work.

The current study proposal aims to implement a clinical decision support system for IOH that provides both automated notifications and contextual information. The decision support aims to educate anesthesia providers about the risks that are associated with IOH. Their response to that decision support will allow us to study blood pressure management by anesthesia provid-

---

\* a MAP of 60 mmHg corresponds with a blood pressure of systolic 80 over diastolic 50 mmHg

ers, the effect of decision support on that blood pressure management, and the subsequent impact on postoperative adverse events.

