## Methods

### Design and participants

#### *Domain*

Adult elderly patients scheduled for a non-cardiac surgical procedure with a moderate to high surgical risk that have a low blood pressure (IOH) during the procedure.

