A more efficient way would be to compare patients that would be *at risk of IOH* rather than patients that would *definitely have had IOH*. A good example is comparing patients with different predicted risks when a prediction model is implemented to prevent postoperative nausea and vomiting. For IOH there is unfortunately no prediction model available. However, when IOH is prevented from occurring because of the implemented decision support, it is likely that they will have a low blood pressure that is just above the threshold. Patients that have a blood pressure below a higher threshold will thus be at risk of a blood pressure below a lower threshold, if it weren't for the intervention by the anesthesia providers. The next crucial step would be to select that higher threshold. Selecting too high a threshold will dilute the effect, whereas too low a threshold and patients may drop out because they are prevented from reaching that threshold. Although one cannot be sure what would be the best threshold in advance, it seems reasonable that a mean arterial pressure (MAP) below 65 mmHg would be a reasonable indication of MAP below either 60 mmHg or 55 mmHg.

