### *Postoperative feedback emails*

The first two elements consist of the same email notification aimed at different anesthesia providers: the attending anesthesiologists or the in-room providers. The anesthesia providers will be notified within 24 hours after the end of a case, when the patient had an episode of IOH that is associated with an increased risk of organ injury due to organ ischemia. The feedback email will primarily report the risk of AKI at VUMC. In addition, the feedback emails will include a link to a more detailed description of all organ risks (see Table 2 and the Example for the Feedback emails). Moreover, at the end of each week, the anesthesia providers will receive an email that reports which of their patients suffered from postoperative AKI or myocardial injury that week (such a report is already a part of clinical routine at VUMC). As the follow-up for AKI is seven days, the update may contain patients that had their procedure during the previous 14 days.

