### *Triggers of near real-time notifications*

The near real-time notifications systems will be triggered by a MAP below 60 mmHg (Figure 2). The decision support system will then provide a notification of the AKI risk at VUMC. Depending on how much time the MAP of an individual patient was below a particular threshold, the notification will display the risk of organ ischemia for that patient (mild, moderate or high, see Table 2). An example in time is shown in Figure 2 – examples 1 and 2.

The near real-time notifications for the in-room providers will be continuously displayed within the AIMS. The near real-time notifications for the anesthesiologists will be sent to their pagers. The pager notifications will repeat with a 10-minute interval. Within a single episode of IOH there will be a maximum of four notifications the paging system (Figure 2 – example 3). An episode of IOH is defined as the time that a patient’s MAP drops below 60 mmHg and the first time it reaches a MAP of 60 or higher. When blood pressure has not returned to normal after the four notifications – i.e. after 40 minutes – it is assumed that there is a reason for not increasing the blood pressure. In that instance either the MAP is considered to be appropriate for that patient or the interventions are not sufficiently effective. This prevents anesthesiologists to keep getting notifications throughout the procedure. Even when a new duration threshold is reached, the system will not provide a new notification if four notifications within that episode have already occurred. However, when the blood pressure normalizes for more than 20 minutes, a subsequent IOH episode will again provide notifications to the low MAP. Any risk that is presented, is based on all the previous low MAP values and durations that occurred during the case (Figure 2 – example 4).

Figure 2 - Triggers of near real-time notifications

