### *General education*

All attending anesthesiologists and in-room providers will be informed at the start of the nested trial period – or when they enter the study at a later time – of the study’s purposes and how the decision support will work. The information will be provided by email as well as during scheduled educational sessions for each provider group. Further educational sessions will be scheduled when required.

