#### *Secondary end points: process level*

In contrast to the primary end point and other secondary patient outcome, clustering at the attending level is expected for process level end points. Quantitative analysis on process level end points will thus account for clustering using segmented regression models that also included random effects. For these mixed effects models we will exclude attending anesthesiologists with a low case volume of eligible procedures from the analysis.

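### The primary set is selected on intraoperative MAP below 65 mmHg, measured after the intervention is in place, and no planned analysis checks whether that set stays comparable across periods

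*Combined protocol and SAP*

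**What the plan says.** Under Statistical analysis, Primary end points, the AKI analysis is "performed under the intention-to-treat principle, and only include patients that have had a MAP below 65 mmHg for at least one minute" during the procedure, with segmented regression across a 36-month preintervention and a 9-month intervention period. The Study population section has no MAP condition. The condition comes from the Domain section, which speaks of patients "that have a low blood pressure (IOH) during the procedure", and from Patients at risk of IOH, which argues that a MAP below 65 marks patients at risk of going below 60 or 55.

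That last section also states the hazard: "too low a threshold and patients may drop out because they are prevented from reaching that threshold". It adds that the best threshold cannot be known beforehand.

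On how the intervention could act:
- Alerts: "The near real-time notifications systems will be triggered by a MAP below 60 mmHg".
- Emails: "The anesthesia providers will be notified within 24 hours after the end of a case", when the patient had a relevant hypotensive episode.
- Education: "All attending anesthesiologists and in-room providers will be informed at the start of the nested trial period".
- Carry-over, from the Introduction's discussion of an earlier trial in which providers received notifications for some patients: "is it likely that the provider will be more aware of the blood pressure threshold during a next case".

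The incidence, depth and duration of hypotension are process-level end points, to be analysed with segmented mixed models because "clustering at the attending level is expected for process level end points".

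**The concern.** Membership of the primary set is decided by a measurement that the intervention may influence. If providers who have had education, emails or earlier alerts treat falling pressure sooner, some patients who would have gone below 65 never do, and they leave the intervention-period set. The preintervention set has no such losses. The two periods then differ in who is counted as well as in how patients were treated, and the primary odds ratio (OR) mixes both.

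The direction depends on the AKI risk of those who leave. If it is below the average of the set, the remaining rate rises and the OR moves towards no effect or harm. If it is above the average, the OR moves towards spurious benefit. If both share and case mix are stable, there is no bias.

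The planned hypotension end points would show part of a pressure shift, but a hypotensive episode is defined at MAP below 60, and the population for those end points is not stated. If they are computed only within the MAP<65 set, they cannot show patients leaving it. The MAP<65 items among the behavior end points are drug concentrations during episodes and time to first intervention, not a patient share. The 60% share under Sample size calculation is historic only.

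**Working it through.** **Inputs from the plan (Sample size calculation, Table 3).** MAP<65 share 60%; AKI 9.8% in that set; 43% of the set with MAP<60 for 10 minutes; OR 1.8 for such exposure; overall treatment OR 0.78; 8,019 preintervention and 2,005 intervention procedures (1,671 before the 20% margin); 275 procedures per month.

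**Assumptions, given nowhere in the plan.** s = fraction of would-be members kept above 65 in the intervention period (5% or 10%, so the share falls from 60% to 57% or 54%). r = their AKI risk (5% to 12.8%). r0 = AKI risk in the other 40% of eligible procedures (5% to 8%).

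**1. The plan's sample size.** Two proportions, pooled variance, two-sided 0.05, power 0.80, ratio 7.5/36. With 0.78 used as a risk ratio (9.8% versus 9.8% × 0.78 = 7.64%), this gives 8,010 and 1,669, against 8,019 and 1,671 stated. With 0.78 as an OR (9.8% versus 7.81%), it gives 9,486 and 1,977, which does not match. At 8,019 and 2,005, power is 86% on the first reading and 79% on the second, so both are carried forward.

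**2. Risks implied by the plan.** Let a be the risk without and b the risk with prolonged MAP<60, where odds(b) = 1.8 × odds(a). Solving 0.57a + 0.43b = 0.098 gives a = 7.5% and b = 12.8%.

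**3. Bias with no true effect.** AKI rate in the remaining set = (p − s·r)/(1 − s), with p = 0.098, compared with 0.098. Example: s = 10%, r = 5% gives (0.098 − 0.005)/0.90 = 10.33%, OR 1.061.

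| s | r = 5% | r = 7.5% | r = 12.8% |
|---|---|---|---|
| 5% | 1.029 | 1.014 | 0.982 |
| 10% | 1.061 | 1.029 | 0.962 |

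The sign changes at r = 9.8%. The two-group standard error of the log OR is about 0.084 to 0.091, so the bias is at most 0.7 standard errors at s = 10% and 0.3 at s = 5%.

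**4. Bias and power with a true effect.** Same formula, with p = 0.0781 (OR) or 0.0764 (risk ratio), and 2,005 × (1 − s) intervention procedures. On the OR reading, s = 10% gives an observed OR of 0.81 (r = 5%) to 0.78 (r = 7.5%). Two-group power for r from 5% to 7.5%:

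| Reading of 0.78 | s = 0 | s = 5% | s = 10% |
|---|---|---|---|
| OR | 79% | 71–77% | 60–74% |
| Risk ratio | 86% | 79–84% | 70–82% |

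Part of this is lost numbers. On the OR reading with unbiased rates, losing 10% of intervention procedures (2,005 to about 1,804) takes power from 79% to 76%.

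**5. The plan's own effect model.** If all prolonged hypotension is prevented, b becomes a, and everyone in the set has 7.5% risk. Leavers and stayers then have the same risk. The OR is (0.0754/0.9246)/(0.098/0.902) = 0.75 whoever leaves, so there is no bias.

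**6. What a share check could detect.** Binomial variance at 0.60, 36 + 9 equal months, 80% power (2.80 × SE), before clustering. It is unclear whether 275 per month is counted before or after the MAP filter, so 275 and 275/0.6 = 458 are both used.
- Trend plus level: SE 0.0153 and 0.0118, detectable fall 4.3 and 3.3 points (s about 7% and 5.5%).
- With slope change: SE 0.0208 and 0.0161, detectable fall 5.8 and 4.5 points (s about 10% and 7.5%).
- An assumed design effect of 1.5 multiplies these by 1.22: 4.1–5.2 and 5.5–7.1 points.

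**7. All-eligible AKI analysis.** Risks 0.6 × 0.098 + 0.4·r0 versus 0.6 × 0.0781 + 0.4·r0. For r0 = 5%: 7.88% versus 6.69%, OR 0.84. For r0 = 8%: 9.08% versus 7.89%, OR 0.86. Over 9,900/2,475 to 16,500/4,125 procedures, power is 46–74% (two-group), 26–46% (trend plus level) and 16–27% (with slope change).

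**The case against.** The restriction is a deliberate at-risk definition, openly stated and argued for. The 5 mmHg gap between the alert trigger and the selection threshold is a buffer: a patient who triggers an alert has already been below 65. This stands, and it rules out a reading a reader might infer, that alerts directly remove the patients they fire for. Membership can change mainly through emails, education and carry-over to later patients.

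The plan also has partial safeguards. Hypotension incidence is to be compared overall and conditional on decision-support activity, depth and duration are end points, and the primary analysis section mentions multivariable modelling and descriptive statistics. It would therefore be too strong to say that the plan can show nothing about a shift in pressure. None of these provisions, however, specifies the MAP<65 share or the case mix of the set by period, and the model covariates are not listed.

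The 20% margin absorbs a pure loss of numbers up to 16.7% (2,005 to 1,671). That also stands, but a margin on numbers does not correct bias.

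Finally, the plan considered analysing all patients and rejected it because of dilution. That is a sound reason not to make it primary. It does not exclude a supportive analysis that does not depend on the filter. The share check is also imperfect: it can miss departures up to about 10%, more if clustering is strong; ordinary changes in practice could move the share; and a stable share does not prove stable case mix.

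**Conclusion.** The concern holds as an untested assumption that the plan itself raises, of minor to moderate priority. The bias is of unknown size and probably small: with s of 5% to 10% and r of 5% to 12.8%, both assumed, a null OR is seen as 0.96 to 1.06. The power loss depends on s, r and the reading of 0.78, and part of it is lost numbers rather than bias. All power figures in that comparison are two-group approximations that ignore trend and autocorrelation.

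Three stronger readings are not supported. The documents do not show that the set is in fact unstable, since they give neither s nor r. They do not fix a direction of bias, and under full prevention as the plan models it there is none. Nor does the intention-to-treat wording invalidate the analysis: the same sentence states the restriction, so the label is a matter of wording.

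**What to change.** Prespecify two additions.

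1. Report the proportion of all eligible procedures with MAP below 65 for at least one minute, by period. Fit it with the segmented mixed model already planned for process-level end points and give the confidence interval. Beside it, tabulate the preoperative Table 4 variables of the MAP<65 set by period.
2. Add a supportive AKI analysis of all eligible procedures, using the same segmented model as the primary and reported with its confidence interval. State that it neither replaces nor gates the primary analysis, and that a null or discordant result there does not refute it.

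Optionally, describe the primary set as an at-risk set defined by intraoperative MAP<65 and analysed by study period.

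The cost is one table, two model fits and some wording, on routinely collected data. The price in interpretation is a diluted, low-powered supportive estimate and a share check that cannot exclude small departures; the plan should say both in advance.

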#### *Secondary end points: patient outcome*

Secondary patient outcomes will be primarily performed similar to the primary end point. For continuous end points, either a parametric or a nonparametric approach will be used as is appropriate to the distribution of the end points.

#### *Secondary end points: process level*

In contrast to the primary end point and other secondary patient outcome, clustering at the attending level is expected for process level end points. Quantitative analysis on process level end points will thus account for clustering using segmented regression models that also included random effects. For these mixed effects models we will exclude attending anesthesiologists with a low case volume of eligible procedures from the analysis.

#### *Secondary end points: behavior*

The impact of the decision support system on the blood pressure management of patients will also be studied. This will be done by observing changes in the usage patterns of various treatment options, such as reducing anesthesia, administering vasoactive or inotropic drugs, and administering intravenous fluids. The analysis of fluid administration is expected to be restricted by the accuracy of the AIMS.

Because of the intricate relation between the occurrence of IOH and the timing of various treatment options, there is currently no straightforward method to analyze the effect of the decision support on blood pressure management. Methods for analyzing the behavioral patterns in response to blood pressure thresholds will be explored in a separate observational study. This study has already been initiated through the MPOG initiative and is expected to be completed before the end of the study period. The findings within this study will determine how treatment behavior should be defined and studied within the present decision support study. If necessary, the study proposal will be amended accordingly.

### *Additional analyses: specific clinical research questions*

The previous paragraphs describe the analyses of the differences in various end points between different study periods. The research questions as described in ‘Specific clinical research questions’ require additional analyses on the relation between depth and duration of IOH and the patient and process level end points. The goal of these additional analyses is to study the relation between IOH, treatment and outcome. The relation between IOH and various end points will be compared between the preintervention and intervention phases. This may seem as a very complex way to study the relation between IOH, treatment and outcome. However, as treatment is an intermediate variable between IOH and outcome, there is no straightforward mathematical way to analyze this relationship using observational data alone. The expected differences between the preintervention and intervention phases will be the changes in blood pressure measurement. The comparison between these phases will thus allow studying of the relation between IOH and various end points may relate to treatment of IOH. As this relation will depend on various preoperative and intraoperative factors, several effect modifiers will be considered (Table 4).

Within the scientific literature there is a large variation in how IOH is defined and analyzed. Different thresholds are used for either systolic, mean or diastolic blood pressure, or even multiple thresholds for a given combination. In addition to a threshold definition, the variable for IOH can also be modelled in several ways. The thresholds often introduce a cut-off: anything above the threshold is considered ‘zero’. All values above the threshold are considered to be the same, even when they are close to the threshold. However, everything below the threshold can be modelled in several ways: duration of blood pressure below the threshold, the area under the threshold (AUT), or simply a ‘one’ – i.e. ‘yes’ the patient’s blood pressure was below the threshold. In a separate observational study we aim to evaluate what the best way is to define and analyze hypotension as an independent variable. This observational study is expected to be completed before the end of the present decision support study. The results of this observational study will be used to guide the analysis of the relation between IOH and patient and process level end points.

Table 4 - Variables that will be considered as effect modifiers during the analysis

Preoperative patient condition
Age
ASA physical status or functional status
Cardiovascular comorbidity
Hypertension
Diabetes Mellitus
History of cardiac disease
History of cardiovascular disease
Non-end-stage renal disease
Intraoperative patient condition
Other vital signs
Heart rate
Oxygen saturation
Pulse pressure variation
Blood loss
Procedural factors
Surgical phase (induction / surgical preparation / surgical)
Type of anesthesia (general anesthesia / central neuraxial blockade)
Type of surgery (vascular, neurosurgery, orthopedic, trauma, ENT)
Emergency surgery
Anesthetic depth
Duration of surgery (stratification for duration < 1 hour, between 1 – 3 hours and > 3 hours)

### *Additional analyses: specific decision making questions*

These additional analyses will main consist of analyzing differences in process level and behavior level end points between the various study phases, including the nested cluster-randomized trial. Effect modification by the variables of Table 4 will also be studied.

